8.2. Duration of Exposure to IMP

Duration of treatment (days treated) is the number of days on treatment based on the 1st IMP administration day and end of treatment (EOT) visit day (EOT visit day – 1st day of IMP + 1). For participants who completed trial, EOT date is estimated as the date of visit 5. For participants who did not complete the trial and were not lost to follow-up, their EOT date is estimated as the date of trial discontinuation. For participants who did not complete trial, EOT date is estimated as the date of the last dose of IMP +27.

Number (%) of participants receiving 1 dose, 2 doses, and 3 doses will be summarized using descriptive statistics by treatment group. Duration of treatment (days) will also be summarized using descriptive statistics for each treatment group.

8.3. IMP Compliance

Not applicable.

8.4. Adverse Events

All adverse events will be coded using the Medical Dictionary for Regulatory Activities (MedDRA).

For adverse event recording, the trial period is defined for each participant as the time period from signature of the informed consent form through completion of visit 5 or the early withdrawal visit for participants who withdraw from the trial for any reason.

Adverse events will be collected at each visit via adverse event inquiry.

The following are considered protocol-defined adverse events of special interest to be sent to the Sponsor's Pharmacovigilance Department for evaluation: ophthalmic related adverse events of at least moderate severity and severe hypersensitivity or anaphylactic reactions.

An adverse device effect is an adverse event related to the use of an investigational medical device or combination product. The full definition is provided in the trial protocol.

Events of possible drug-induced liver injury (AST or ALT $\geq 3 \times$ the ULN, total bilirubin $\geq 2 \times$ the ULN), or Hy's Law events, as well anaphylaxis and hypersensitivity reactions will be assessed. Hypersensitivity reactions will be monitored using the diagnostic criteria for anaphylaxis as

outlined by the 2006 Joint National Institute of Allergy and Infectious Disease/Food Allergy and Anaphylaxis Network Second Symposium on Anaphylaxis ([Sampson et al, 2006](#)). In the event of suspected anaphylaxis, vital signs, including oxygen saturation and respiration rate, will be measured.

Summaries by treatment group will be presented for treatment emergent adverse events (overall and by severity), treatment emergent adverse device effects, treatment emergent adverse events determined by the investigator to be treatment-related adverse events (overall and by severity), adverse events determined by the investigator to be related to test IMP (and/or PFS) (ie, reasonable possibility) (defined as related or with missing relationship) (overall and by severity), serious adverse events, serious adverse device effects, protocol-defined adverse events of special interest, adverse events causing discontinuation from the trial, adverse device effects causing discontinuation from the trial, non-serious treatment emergent adverse events and prior to treatment adverse events. Additionally, the injection site reactions recorded as adverse events requiring concomitant or special treatment given and protocol defined adverse events of special interest will be summarized by treatment group separately.

The incidence of adverse event will be summarized using descriptive statistics by SOC, PT, and severity of the adverse event. Each participant will be counted only once within a SOC or a PT by using the adverse events with the highest severity within each category. Treatment-related adverse event summaries will include adverse events related to IMP and adverse events with missing relationship to IMP. Adverse events with the missing flag indicating serious will be excluded from the summary of serious adverse events but included in the summary of non-serious adverse events.

Listings for deaths, adverse events, adverse device effects, serious adverse events, serious adverse device effects, serious adverse events additional information, adverse events leading to discontinuation, adverse device effects leading to discontinuation, injection site related adverse event requiring concomitant or additional treatment given and protocol defined adverse events of special interest will be presented. All information pertaining to adverse events noted during the trial will be listed by subject, detailing verbatim given by the investigator, PT, SOC, date of onset, date of resolution, severity, and relationship to treatment. The onset of adverse events will also be shown relative (in number of days) to the 1st day of treatment. In addition, MedDRA dictionary terms for adverse event descriptions, and adverse event preferred terms by participant number and treatment group will be presented.

All adverse events summary tables will be split by the subgroups of 6-11 years, 12-17 years and overall.

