#### **8.4.4. Recording of Adverse Events and Serious Adverse Events**

All adverse events that occur during the defined trial period must be recorded both on the source documentation and the CRF, regardless of the severity of the event or judged relationship to the IMP (and/or PFS). The Investigator will record all relevant information regarding every adverse event/serious adverse event and will categorize each as guided in [Figure 2](#). For serious adverse events and protocol-defined adverse events of special interest for expedited reporting to Global PV, the Serious Adverse Event and Protocol-Defined Adverse Events of Special Interest Form must be completed and the serious adverse event and the protocol-defined adverse events of special interest must be reported within 24 hours (Section [8.4.7](#)). The Investigator does not need to actively monitor participants for new adverse events after the end of the trial.

[figure not shown]
Serious adverse events and/or serious adverse device effects occurring in a participant after the end of trial should be reported to the Sponsor if the Investigator becomes aware of them, following the procedures described in Section [8.4.7](#).

The onset and end dates, duration (in case of adverse event duration of less than 24 hours), action taken regarding IMP (and/or PFS), treatment administered, and outcome for each adverse event must be recorded on both the source documentation and the CRF.

The relationship of each adverse event to IMP (and relationship to the device, if applicable), and the severity and seriousness of each adverse event, as judged by the Investigator, must be recorded.

The Investigator should make an initial determination whether the adverse event may be related to a device deficiency, using [Figure 2](#), [Table 4](#), and [Table 5](#).

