#### **8.4.6. Reporting of Serious Adverse Events**

To satisfy regulatory requirements, the Investigator must report all serious adverse events that occur during the trial, regardless of the judgment of relationship to administration of the IMP (and/or PFS), to the Sponsor except for serious adverse events listed in Section [8.4.9](#). The Investigator must report the event within 24 hours of learning about it. Completing the Serious Adverse Event Form and reporting the event must not be delayed, even if not all the information is available.

The Serious Adverse Event Form should be sent to the Local Safety Officer (LSO) or designee (as applicable, for eg, a contract research organization [CRO]) in a country without a Sponsor LSO; the LSO will forward the report to the Sponsor's Global PV.

Each report of a serious adverse event will be reviewed and evaluated by the Investigator and the Sponsor to assess the nature of the event and the relationship of the event to the IMP (and/or PFS), trial procedures, and to underlying disease.

The Investigator should forward additional information (follow-up) about any serious adverse event unavailable at the initial reporting within 24 hours of when it becomes known, following the same process as for the initial report.

The process for serious adverse device effect reporting to Global PV is the same as for serious adverse event reporting.

The following information should be provided to record the event accurately and completely:

- trial number
- Investigator and investigational center identification
- participant number
- onset date and detailed description of adverse event

- Investigator's assessment of the relationship of the adverse event to the IMP (no reasonable possibility, reasonable possibility)

Additional information includes:

- age and sex of participant
- date of first dose of IMP
- date and amount of last administered dose of IMP
- action taken
- outcome, if known
- severity
- explanation of assessment of relatedness
- concomitant medication (including doses, routes of administration, and regimens) and treatment of the event
- pertinent laboratory or other diagnostic test data
- medical history
- results of dechallenge/rechallenge, if known
- for an adverse event resulting in death
  - cause of death (whether or not the death was related to IMP)
  - autopsy findings (if available)

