### **9.4. Analysis of Exploratory Objective(s)**

### **9.5. Safety Analyses**

Safety analyses will be performed on the safety analysis set (Section 9.1.1).

Safety assessments and time points are provided in [Table 1](#).

All adverse events will be coded using the Medical Dictionary for Regulatory Activities. Each participant will be counted only once in each preferred term or system organ class category for the analyses of safety. Summaries will be presented for all adverse events (overall and by severity), adverse events determined by the Investigator to be related to test IMP (and/or PFS) (ie, reasonable possibility) (defined as related or with missing relationship) (overall and by severity), serious adverse events, serious adverse device effects, protocol-defined adverse events of special interest, adverse events, and adverse device effects causing withdrawal from the trial. Summaries will be presented by treatment group and for all participants. Participant listings of serious adverse events, serious adverse device effects, adverse events, and adverse device effects leading to withdrawal will be presented.

Changes in laboratory, ECG, and vital signs measurements data will be summarized descriptively. All values will be compared with predefined criteria to identify potentially clinically significant values or changes, and such values will be listed.

Suicidal ideation and behavior will be measured using the C-SSRS. Data for participants with positive findings will be listed.

The use of concomitant medications will be summarized by therapeutic class using descriptive statistics. Concomitant medications will include all medications taken while the participant is treated with IMP.

For continuous variables, descriptive statistics (n, mean, SD, median, minimum, and maximum) will be provided for actual values and changes from baseline to each time point. For categorical variables, participant counts and percentages will be provided. Descriptive summaries of serious adverse events, participant withdrawals due to adverse events, and potentially clinically significant abnormal values (clinical laboratory or vital signs) based on predefined criteria will be provided as well.

If any participant dies during the trial, a listing of deaths will be provided, and all relevant information will be discussed in the participant narrative included in the CSR.

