### **11.2. Data Quality Assurance**

Refer to Section 8.6 for the definition of a clinical product complaint or device deficiency and Investigator responsibilities in the management of a clinical product complaint or device deficiency. Further details are given in a Pharmacy Manual.

Data Management is responsible for the accuracy, quality, completeness, and internal consistency of the data from this trial.

Oversight will be carried out as described in the Sponsor's SOPs for clinical trials. Day to day data management tasks for this trial are delegated to a contract organization, and these functions may be carried out as described in the SOPs for clinical trials at that organization. These SOPs will be reviewed by the Sponsor before the start of data management activities.

Data will be verified by the trial monitor using the data source, and reviewed by Data Management using both automated logical checks and manual review. Data identified as erroneous, or data that are missing, will be referred to the investigational center for resolution through data queries. Any necessary changes will be made in the clinical database, and data review and validation procedures will be repeated as needed. Data from external sources will be compared with the information available in the Clinical Data Management System (CDMS) and any discrepancies will be queried.

CRFs received will be processed and reviewed for completeness, consistency, and the presence of mandatory values. Applicable terms will be coded according to the coding conventions for this trial. Logical checks will be implemented to ensure data quality and accuracy. Any necessary changes will be made in the clinical database, and data review and validation procedures will be repeated as needed. Data from external sources will be compared with the information available in the CDMS. Discrepancies found will be queried.

Data corrections in the CDMS will be made using the CDMS update function. The system requires a reason for each change and keeps a complete audit trail of the data values, dates and times of modifications, and authorized electronic approvals of the changes.

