8. SAFETY ANALYSIS

8.1. General

The safety population will be used for all safety analyses. Summaries will be presented by treatment group (TEV-48125 225 mg, TEV-48125 120 mg and placebo). TEV-48125 will be presented as actually received unless specified otherwise. A total column will also be provided.

For continuous variables, descriptive statistics (n, mean, SD, median, minimum, and maximum) will be provided for actual values and changes from baseline to each time point. For categorical variables, participant counts and percentages will be provided.

Missing values will be reported as missing and no imputation will be undertaken.

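### Adverse events with a missing seriousness flag are tabulated as non-serious, which conflicts with the SAP's own rule that missing safety values are reported as missing

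*SAP*

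**What the plan says.** SAP 8.4 treats two kinds of missing adverse event information in adjacent sentences. For causality, "Treatment-related adverse event summaries will include adverse events related to IMP and adverse events with missing relationship to IMP". For seriousness, "Adverse events with the missing flag indicating serious will be excluded from the summary of serious adverse events". The rest of that sentence moves such events to the non-serious table.

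The causality rule comes from the protocol. Protocol 9.5 describes the related-event summaries as "defined as related or with missing relationship". Protocol 9.5 has no corresponding rule for seriousness, so that rule originates in the SAP.

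SAP 8.1, which governs all the safety analyses, says: "Missing values will be reported as missing and no imputation will be undertaken".

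On data collection, Protocol 8.4.4 requires that "the severity and seriousness of each adverse event, as judged by the Investigator, must be recorded". Protocol 11.2 says that "CRFs received will be processed and reviewed for completeness, consistency, and the presence of mandatory values", and sends missing data back to the centre as queries. Serious events also go on a separate form (Protocol 8.4.3), and under Protocol 8.4.6 "The Investigator must report the event within 24 hours of learning about it".

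**The concern.** A blank seriousness flag means that the investigator's judgement is not in the database. The SAP turns that blank into a definite classification, and the classification is the reassuring one. Protocol 8.4.1.2 regards an event as nonserious when it meets none of the listed criteria, and an empty field does not establish that.

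No reason is given for resolving the two gaps in opposite directions, or for departing from SAP 8.1. At stake is the reading of two tables. The serious-event summary could omit an event that was serious, and the non-serious summary could include events whose seriousness is unknown. No planned table shows how many such events there are. The fields that SAP 8.4 names for the adverse event listing do not include seriousness, although that sentence opens by promising all information on adverse events.

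**Working it through.** The documents give no figure on this point, so there is nothing to reproduce. The check is a comparison of the rules, followed by a bound on the error.

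**Rules side by side**

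| Missing item | Rule | Source | Agrees with SAP 8.1? |
|---|---|---|---|
| Relationship to IMP | Counted as related | Protocol 9.5, SAP 8.4 | No; errs towards caution |
| Seriousness | Counted as non-serious | SAP 8.4 only | No; errs towards reassurance |
| Safety values in general | Left as missing | SAP 8.1 | – |

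Both specific rules depart from the general one. The causality rule has the protocol behind it and the seriousness rule does not.

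**Bound within a treatment group**

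Let S be the number of participants with at least one event flagged serious. Let m be the number of further participants who have no flagged serious event but at least one event with a blank flag at lock.

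- Reported count under SAP 8.4: S.
- True count T: between S (no blank hides a serious event) and S + m (every one of the m participants had a serious event).
- Error, reported minus true: S − T, which lies between −m and 0.

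The error is never positive. With m = 0 it is zero. The non-serious count carries an error of the opposite sign, zero or positive. The same argument applies within each system organ class or preferred term. Because SAP 8.4 counts a participant once per category, a blank-flag event in someone already counted as serious in that category adds nothing.

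**Bound on the difference between groups**

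For test IMP (t) and placebo (p) with denominators n_t and n_p, the reported difference is D = S_t/n_t − S_p/n_p. The true difference lies between D − m_p/n_p and D + m_t/n_t. That interval extends on both sides of D whenever both groups have blanks.

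Illustration with assumed counts: two flagged participants in each group, plus two participants whose serious events are hidden by blank flags. The SAP rule reports 2 against 2 in every case.

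- Both hidden cases on test IMP: the truth is 4 against 2.
- Both on placebo: the truth is 2 against 4.
- One in each group: the truth is 3 against 3.

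**The case against.** The strongest reply is that the rule will seldom, if ever, apply. Seriousness is a required item, CRFs are checked for required values, and blanks are queried. Protocol 11.2 also compares external data with the clinical database and describes lock as confirmation that all data have been captured. A serious event has a second route to the sponsor through its own form and 24-hour deadline, and deaths are listed separately. A true serious event would be lost from the table only if the flag stayed blank through all of this. That stands, and it is why the expected effect is zero or very small. It does not justify the default for a blank that survives.

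A second reply is that the two gaps differ in kind. Relationship is a judgement, whereas seriousness turns largely on defined outcomes and has its own reporting route, so a blank flag with no serious event form points towards non-serious. This has some force. It is an argument for checking the blank against the safety database. It does not support classifying the event as non-serious without that check.

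A third reply is that affected events remain in the overall and by-severity tables. That is true, but a reader of those tables cannot tell that seriousness was unknown.

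Four stronger readings are tempting, and the documents support none of them:

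- A reader might infer that the rule favours test IMP in the comparison with placebo. The bound above shows that the difference can move in either direction.
- A reader might divide one participant by the 139 planned per group to size the effect. That is the number randomized. The safety tables use the safety set in separate 225 mg, 120 mg and placebo columns (SAP 8.1), and adverse event tables are also split by age (SAP 8.4). The documents do not give those denominators.
- A reader might link the point to the absence of a data monitoring committee. The rule concerns end-of-trial tables. Review of serious events during the trial (Protocol 7.4 and 8.4.6) works from reported events and does not use it.
- A reader might conclude that every blank should be counted as serious. That would also be an imputation contrary to SAP 8.1, and it could overstate the serious-event count.

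**Conclusion.** The point holds as a minor one. SAP 8.4 states a rule that assigns unknown seriousness to the reassuring category. The rule runs opposite to the adjacent causality rule, has no basis in Protocol 9.5 and is inconsistent with SAP 8.1.

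Its consequence is limited to serious-event counts within each treatment group, which can be too low by at most the number of participants whose only possible serious event has a blank flag. No percentage can be attached, because neither the number of blanks nor the table denominators are given. The effect is zero if all flags are complete at lock, and the protocol's safeguards make that likely. Even where a blank remains, there is an error only if the event was in fact serious. The primary and secondary efficacy analyses are unaffected.

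**What to change.** Replace the sentence in SAP 8.4 so that events with missing seriousness are not counted as non-serious. In its place:

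1. Before lock, reconcile every blank flag against the safety database and query those that remain.
2. Show any residual events in a separate row, labelled as seriousness missing, by treatment group.
3. Give the serious adverse event incidence twice, without and with these events.
4. State in SAP 8.1 that the missing-relationship rule, which comes from the protocol, is an exception to reporting missing values as missing.

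The note to file at the end of the SAP says that the trial analysis has already been conducted. If so, the practical step is to state in the clinical study report how many flags were blank at lock in each treatment group and, if any were, to show the serious-event counts both ways. Protocol section 9 already provides for disclosing changes made after the SAP was final.

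The cost is one revised sentence, one extra table row, and a worst-case serious-event count that may be slightly higher. If no flag is blank, no table changes.

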8.5. Deaths

If any participant dies during the trial, a listing of deaths will be provided, and all relevant information will be discussed in the participant narrative included in the clinical trial report.

8.6. Clinical Laboratory Tests

Clinical laboratory tests (serum chemistry, hematology, coagulation, and urinalysis) will be performed using the central laboratory at the time points detailed in the trial protocol. Specific laboratory tests to be performed are listed below in [Table 3](#).

Table 3: Clinical Laboratory Tests

Serum chemistry	Hematology and coagulation	Urinalysis
Calcium	Hemoglobin	Color and appearance
Phosphate	Hematocrit	Protein
Sodium	RBC count	Glucose
Potassium	RBC indices	Ketones
Chloride	mean corpuscular volume	Blood
Creatinine	mean corpuscular hemoglobin concentration	Leukocyte esterase
Glucose	RBC distribution width	Nitrite
BUN	Platelets	Bilirubin
ALT	Leukocytes	pH
AST	neutrophils	Specific gravity
LDH	lymphocytes	Microscopic tests
GGT	eosinophils	bacteria
Alkaline phosphatase	monocytes	erythrocytes
Creatine phosphokinase	basophils	leukocytes
Carbon dioxide	Prothrombin time	crystals
Magnesium	Partial thromboplastin time	casts
Protein	INR	
Albumin		
Bilirubin (total and direct)		

ALT=alanine aminotransferase; AST=aspartate aminotransferase; BUN=blood urea nitrogen; GGT=gamma-glutamyl transpeptidase; INR=International Normalized Ratio; LDH=lactate dehydrogenase; RBC=red blood cell.

Laboratory tests results and changes from baseline for chemistry, hematology, urinalysis, and coagulation laboratory tests will be summarized by visits for each treatment group using descriptive statistics. Shifts (below, within, and above the normal range) from baseline to each visit and Last Assessment will be summarized using participant counts. Listings of all individual participants' laboratory test results will be presented.

All clinical laboratory test results outside of the reference range will be judged by the Investigator as belonging to one of the following categories:

- abnormal and not clinically significant
- abnormal and clinically significant

A laboratory test result that is judged by the Investigator as clinically significant will be recorded both on the source documentation and the CRF as an adverse event. The incidence of potentially clinically significant abnormal results will be summarized using descriptive statistics with the criteria specified in [Table 4](#). The potentially clinically significant abnormal laboratory values will include all postbaseline values (including scheduled, unscheduled, and early termination visits) for the summaries. Listings of participants who have potentially clinically significant abnormal laboratory data will be presented.

Table 4: Criteria for Potentially Clinically Significant Laboratory Values

Test	Pediatric 6-11 Years Criterion Value	Pediatric 12-17 Years Criterion Value
Serum chemistry		
ALT	$\geq 2x$ ULN	$\geq 2x$ ULN
AST	$\geq 2x$ ULN	$\geq 2x$ ULN
ALP	$\geq 3x$ ULN	$\geq 3x$ ULN
GGT	$\geq 3x$ ULN	$\geq 3x$ ULN
LDH	$\geq 2x$ ULN	$\geq 2x$ ULN
BUN	≥ 9.0 mmol/L	≥ 9.0 mmol/L
Creatinine	≥ 100 μ mol/L	≥ 150 μ mol/L
Bilirubin (total)	≥ 34.2 μ mol/L	≥ 34.2 μ mol/L
Hematology		
Hematocrit	Males < 0.30 L/L Females < 0.30 L/L	< 0.32 L/L < 0.31 L/L
Hemoglobin	Males ≤ 100 g/L Females ≤ 100 g/L	≤ 110 g/L ≤ 100 g/L
WBC counts	$\leq 3 \times 10^9$ /L $\geq 20 \times 10^9$ /L	$\leq 3 \times 10^9$ /L $\geq 20 \times 10^9$ /L
Eosinophils	$\geq 10\%$	$\geq 10\%$
ANC	$\leq 1 \times 10^9$ /L	$\leq 1 \times 10^9$ /L
Platelet counts	$\leq 75 \times 10^9$ /L $\geq 700 \times 10^9$ /L	$\leq 75 \times 10^9$ /L $\geq 700 \times 10^9$ /L
Urinalysis		
HGB	≥ 2 unit increase from baseline	≥ 2 unit increase from baseline
Glucose	≥ 2 unit increase from baseline	≥ 2 unit increase from baseline
Ketones	≥ 2 unit increase from baseline	≥ 2 unit increase from baseline
Total protein	≥ 2 unit increase from baseline	≥ 2 unit increase from baseline
Coagulation		
INR	>1.5	>1.5

ALP=alkaline phosphatase; ALT=alanine aminotransferase; ANC=absolute neutrophil count AST=aspartate aminotransferase; BUN=blood urea nitrogen; GGT=gamma- glutamyl transpeptidase; HGB=hemoglobin; INR=international normalized ratio; LDH=lactate dehydrogenase; RBC=red blood cell; ULN=upper limit of normal range; WBC=white blood cell

Serum β -HCG tests will be performed for all female participants who are postmenarchal or ≥ 12 years of age at screening (visit 1) and visit 5; urine β -HCG tests will be performed at all other visits. Any participant who becomes pregnant during the trial will be withdrawn.

